APPENDIX 4: ELECTRONIC VISUAL ACUITY (EVA) AND MANIFEST REFRACTION

1.0 REFRACTION PROTOCOL TECHNIQUE

A. Introduction

ALL refractionists should be proficient in the following optical fundamentals:

- Spherical equivalency
- Plus/minus spheres and cylinders
- Hyperopia, myopia and astigmatism
- "Push plus" refraction principles.

1.1 Refraction Chart

- Use of the refraction chart on the Electronic Visual Acuity Tester (EVA) at a distance of 3 meters is the method of choice for performing refraction (see RVACC Visual Acuity Testing Procedures Manual for EVA details). If the EVA is not working, either ETDRS chart R at 4 meters/1 meter can be used.
- For the EVA, the refraction chart on the EVA is displayed by tapping on the [Chart] icon on the Main Menu of the Palm Handheld or tapping the dropdown in upper right corner of screen and selecting 'EVA Applications'; select [Chart] icon.
- If the EVA is not functioning and the ETDRS chart R is used for refraction, the refraction protocol described beginning in Section B "Steps in Refraction" should be performed, starting at 4 meters. If the subject is unable to read at least 3 letters on both the 20/200 and 20/160 lines, the subject should be moved to 1 meter, a +0.75 diopter (D) sphere added to the spherical power in the trial frame, and the refraction performed using the appropriate lenses according to the vision level. The refraction obtained at 1 meter must be reported as a 4-meter equivalent by subtracting +0.75 (D) from the spherical power.
- Under no circumstances should the ETDRS charts be used interchangeably with the EVA during the same refraction session.

Check the room lighting level before beginning the refraction. For the EVA, dim incandescent lighting is required; fluorescent lighting should not be used. There should be no glare on the EVA screen and no spotlights. After warming up the EVA for at least 10 minutes, it should be calibrated for size and brightness (see RVACC Visual Acuity Testing Procedures Manual for EVA details).

1.2 Trial Frames/Phoropter

- Trial frames are preferred for use in refraction. If trial frames/lenses are not used, a phoropter may be used. If a phoropter is used, the final refraction **MUST** be put in trial frames and the final spherical refinement performed at 3 meters with the EVA, if the EVA is used, or at 4 meters with the ETDRS chart, if the EVA is not functioning.
- If a phoropter is used for a subject whose acuity is worse than 20/80, the ± 0.25 D or ± 0.50 D strength of the phoropter's mounted cross cylinder may not allow the subject to notice any change when checking for cylindrical axis and power. In this case, a separate ± 1.00 D handheld cross cylinder (as in the Protocol Summary at the end of this chapter) held in front of the phoropter instead of the mounted cross cylinder is recommended.

The protocol for the subjective refraction is described in terms of a trial frame, but a similar method can be followed with a phoropter.

The trial frame is placed and adjusted on the subject's face so that the lens cells are parallel to the anterior plane of the orbits and centered in front of the pupils. The left eye is occluded and the starting refraction is placed in the right lens cells, with the cylindrical correction anterior. The steps for the procedure are detailed below.

1.3 Contact Lens Use

If the subject wears contact lenses and has spectacle glasses as well, he/she should be instructed to refrain from wearing the contact lenses on the day of each examination. In the event that the subject either has no glasses or has forgotten the instructions and has reported for the examination wearing contact lenses, these should be removed and at least one-half hour should elapse before the refraction is performed. In this latter event, careful attention should be given to the cornea during the slit-lamp examination; any abnormalities should be noted in the subject's clinic record.

B. Steps in Refraction

1. Determine initial starting refraction
2. Refine sphere for the right eye
3. Refine cylinder axis for the right eye
4. Refine cylinder power for the right eye
5. Recheck sphere for the right eye
6. Repeat the process for the left eye

1.4 Determine Initial Starting Refraction

If subject has had study refraction at a prior visit, use the refraction results from the most recent visit.

If this is the first study refraction for the subject, use one of the following for the starting refraction:

- Retinoscopy
- Autorefractor
- Current spectacles
- Previous refraction (available in subject's chart)

In the exceptional case that none of the above is available, then start the refraction with 'plano.'

The refraction steps below are for visual acuities of 20/20 to 20/80 with the initial starting refraction. For acuities worse than 20/80, refer to the charts for appropriate sphere and cylinder powers to use. Whenever the acuity improves to a better range by improved correction (e.g., from 20/80 – 20/160 range to 20/20 – 20/80 range) smaller sphere and cylinder powers for the better acuity range according to the charts should be used.

1.5 Refine Sphere

a. Increase Plus

	Sphere for Checking	Sphere Incremental Change
20/20 - 20/80	+0.50	+0.50
<20/80 – 20/160	+1.00	+1.00
20/200 – 20/320	+2.00	+1.00
<20/320	+2.00	+1.00

The right eye is tested first and then the left eye. The starting refraction is placed in the trial frame; the left eye is occluded with an occluder lens and tissue or eye patch and the refractionist determines the lowest line that the subject can read.

With the subject focused on the smallest letters that he/she can read, a +0.50 D sphere is held in front of the trial frame over the right eye, and the subject is asked if the lens makes the vision clearer, blurrier, or keeps the vision exactly the same.

NOTE: "Clearer, Blurrier, or No change" preferred but "Better, Worse, or No change" can be used.

- If vision is clearer or there is no change, the sphere in the trial frame is replaced with a sphere that is 0.50 D more plus or less minus.

- The +0.50 D sphere is again held in front of the trial frame over the right eye and the subject is asked again if the lens makes the vision clearer, blurrier, or keeps the vision exactly the same.
- If vision is again clearer or there is no change, the sphere in the trial frame is replaced with a sphere that is 0.50 D more plus or less minus.
- This process of increasing the plus sphere or decreasing the minus sphere in the right eye is repeated until the +0.50 D sphere makes the vision blurrier.
- When the +0.50 D sphere makes the vision blurrier, no additional change in the sphere is made at this time.
- By this process the highest plus or least minus sphere for best vision is determined.

b. Increase Minus

	Sphere for Checking	Sphere Incremental Change
20/20 - 20/80	-0.50 (or -0.37)	-0.25
<20/80 - 20/160	-1.00	-0.50
20/200 - 20/320	-2.00	-1.00
<20/320	-2.00	-1.00

After determining the highest plus or least minus sphere, the subject is asked to read the smallest line possible (the reading should be at least as good as the initial reading).

The -0.50 (or -0.37) D sphere is held in front of the trial frame before the right eye and the subject is asked if the vision is improved so he can actually read more letters.

- If vision is not improved, the +0.50 D sphere is held in front of the trial frame before the right eye once again to see if the subject will accept more plus.
- If the subject reports that the -0.50 (or -0.37) D lens improves vision, the subject is requested to read the smallest line possible while the -0.50 (or -0.37) D lens is held in front of the trial frame.
- If there is an actual improvement in acuity and the examiner is convinced that the subject is able to read at least one additional letter, then the sphere in the trial frame is replaced by a sphere that is 0.25 D less plus or more minus.

Minus spherical power is added in -0.25 D increments in this fashion as long as the subject continues to read at least one additional letter.

- If the subject is unable to read any more letters, the sphere is not changed, even if the subject reports that the vision with the extra minus is better (or sharper and darker or more distinct).

The final check in the initial sphere evaluation should be the presentation of a +0.50 D sphere to determine if any more plus sphere will be accepted initially.

Example: Assume that following the check with plus sphere, the sphere in the trial frame is -0.50. The subject is asked to read the lowest line possible with this correction and reads the 20/20 line perfectly and no letters on the 20/16 line. Then -0.50 (or -0.37) D is held in front of the trial frame and the subject is asked if the lens makes the vision clearer or blurrier. If the subject reports that the vision is clearer, he is again asked to read the chart. If more letters are read (e.g., 20/20+2), then the sphere in the trial frame is changed to -0.75.

The process is repeated with a -0.50 (or -0.37) D added over -0.75. If again the subject reports that vision is improved, but he cannot read any additional letters, the sphere should remain at -0.75 and a final sphere check with a +0.50 D lens done.

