3.2.1 Study Eye Inclusion Criteria

1. The study eye must retain adequate fixation to allow for completion of protocol assessments.
2. The study eye must have macular cystic changes (>275 microns and/or disruption of foveal contour on OCT).

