	c. +2.00	+1.00				c. +1.00	+1.00
<20/320	a. +2.00	+1.00	No cylinder test			No refinement	
	b. -2.00	-1.00					
	c. +2.00	-1.00					

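### One sign in the refraction summary is wrong: for eyes worse than 20/320, step c answers an accepted +2.00 D lens with a -1.00 D change, against table 1.5a

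*Combined protocol and SAP*

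**What the plan says.** Appendix 4, section 1.5, gives two step tables. For eyes worse than 20/320, the Increase Plus table (1.5a) reads "<20/320 +2.00 +1.00": check with +2.00 D and change the sphere by +1.00 D. The accompanying text, worked through for the 20/20 to 20/80 band, fixes the direction: "If vision is clearer or there is no change, the sphere in the trial frame is replaced with a sphere that is 0.50 D more", that is, a move towards plus. Section 1.5 ends with one last plus check, whose purpose is "to determine if any more plus sphere will be accepted initially".

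Section 1.4 sends the refractionist to the charts in poor-seeing eyes: "For acuities worse than 20/80, refer to the charts for appropriate sphere and cylinder powers to use". The Refraction Protocol Summary, which follows section 1.10, condenses the procedure into three sphere steps: a (plus), b (minus) and c (plus again). For eyes worse than 20/320 the row opens with "a. +2.00 +1.00 No cylinder test", continues with -2.00 D and -1.00 D at step b, and at step c pairs +2.00 D with -1.00 D. Its sphere-refinement columns say "No refinement".

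BCVA change is a secondary outcome (section 7.2), and a loss of more than 0.3 logMAR from baseline is a safety-monitoring item (section 6.0). The study-eye criteria set no acuity floor. The nearest requirement is "The study eye must retain adequate fixation to allow for completion of protocol assessments".

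**The concern.** At step c the summary says, in effect, that if the eye accepts more plus, the lens should be made more minus. That is the reverse of what the check is for. The charts are the working instruction for this band, because the worked text in 1.5 uses the smaller lenses of the 20/20 to 20/80 band. Here two charts disagree. For this band the summary also drops the cylinder test and the sphere refinement, so the summary itself contains no later step that would reveal the slip.

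What is at stake is the trial-frame lens through which BCVA is measured in the worst-seeing eyes. Results are presented by participant, with up to five per disease group, so an acuity distorted in one eye would stand in the listing and would not be averaged out. The control eye has no acuity criterion either, yet it is the comparator in section 7.2.

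**Working it through.** No sample-size or power formula applies. The check is an entry-by-entry comparison of the summary with the step tables. Steps a and c are both plus checks and should match table 1.5a. Step b should match table 1.5b. Each cell below gives the checking lens and then the sphere change, in dioptres, as printed in the summary.

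| Acuity band | Step a | Step b | Step c | Table 1.5a | Table 1.5b |
|---|---|---|---|---|---|
| 20/20 to 20/80 | +0.50, +0.50 | -0.50 (or -0.37), -0.25 | +0.50, +0.50 | +0.50, +0.50 | -0.50 (or -0.37), -0.25 |
| worse than 20/80 to 20/160 | +1.00, +1.00 | -1.00, -0.50 | +1.00, +1.00 | +1.00, +1.00 | -1.00, -0.50 |
| 20/200 to 20/320 | +2.00, +1.00 | -2.00, -1.00 | +2.00, +1.00 | +2.00, +1.00 | -2.00, -1.00 |
| worse than 20/320 | +2.00, +1.00 | -2.00, -1.00 | **+2.00, -1.00** | +2.00, +1.00 | -2.00, -1.00 |

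1. Entries compared: 4 bands x 3 steps = 12. Matches: 11. The one mismatch is step c for eyes worse than 20/320.
2. Gap between the two instructions: (+1.00) - (-1.00) = 2.00 D for each accepted step-c check. This is a difference between instructions, not a measured defocus. Read literally, the summary moves the lens 1.00 D towards minus from where steps a and b left it. Table 1.5a would move it 1.00 D towards plus.
3. Which side is the slip: table 1.5a, step a of the same row, step c in the other three bands, and the text on accepted plus lenses and on the final check all point to plus. Nothing in the appendix supports minus.
4. When it can occur: step a is repeated until plus blurs, so acceptance of +2.00 D at step c is expected mainly after step b has added minus, or when the participant answers that nothing changes.

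The check assumes that the printed cell reads as extracted. The neighbouring cells are clean, so a reading fault is unlikely, but the sponsor should look at the source table.

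**The case against.** The strongest reply is that this is a typographical slip with little practical consequence. Most of that stands. Step a of the same row is correct. Appendix 4 requires every refractionist to be proficient in push-plus principles, so a trained examiner may well notice the sign. An eye that reports no change through +2.00 D is insensitive to that lens, so its acuity cost should be small. Section 1.9 describes a general sphere recheck with no acuity limit, although the summary says there is none for this band. Appendix 1, footnote 2, requires refraction whenever the electronic acuity score changes by more than 10 letters. BCVA is a secondary outcome, described without hypothesis tests, and nothing shows that any enrolled eye will be worse than 20/320.

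A reader might infer more than the documents support:

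- **The error compounds over repeated checks.** Section 1.5 calls this the final check of the initial sphere evaluation, so repeated wrong-way moves are speculation.
- **The error carries forward to later visits.** Section 1.4 does say to "use the refraction results from the most recent visit" as the starting point, but the next refraction begins again at step a, which is correct and pushes towards plus.
- **The error would breach the 0.3 logMAR monitoring threshold.** Converting dioptres to logMAR needs pupil size, accommodation and a blur model. The documents give none of these.

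What the reply does not remove is the contradiction itself, in a chart that the protocol tells refractionists to use.

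**Conclusion.** Wrong as written, minor in severity. One of 12 sphere entries in the Refraction Protocol Summary has the wrong sign, and it differs from table 1.5a by 2.00 D for each accepted check. The effect is conditional on three things: an eye worse than 20/320, acceptance of +2.00 D at step c, and literal use of the summary. Such eyes are not excluded by the eligibility criteria, but their number is unknown.

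Manifest refraction is scheduled at Baseline and Week 8. If the visits between them use the Baseline lens (an assumption, since the documents do not say), a Baseline error would largely cancel in the changes at those visits. An error at only one of the two refractions, or in only one eye, would not cancel in the Week 8 change or in the between-eye comparison. The size of any resulting BCVA error cannot be derived from the documents. The primary outcome of related adverse events and withdrawals is touched only through the acuity-loss monitoring item.

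**What to change.** In Appendix 4, Refraction Protocol Summary, row for eyes worse than 20/320, change the step c sphere increment from -1.00 to +1.00. It then agrees with table 1.5a, with step a of the same row and with the other bands, and all 12 entries match. Use the corrected chart for every refraction, both the scheduled ones and those triggered by a change of more than 10 letters. The cost is one character in an appendix and reissue of the chart. No extra testing and no change to the analysis are needed.

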1.6 Refine Cylinder Axis

For purposes of this discussion, only plus cylinder techniques are presented. Minus cylinders may be used instead of plus cylinders to determine the axis and power of the cylinder. If minus cylinders are used, the procedure described must be revised to reflect this change in sign.

If the starting refraction contains a cylinder correction, changes in cylindrical axis are tested by holding a 0.50 D cross cylinder in front of the trial frame (or appropriate cross cylinder based on level of acuity), first with the positive axis 45 degrees to one side of the cylinder axis, and then with the positive axis 45 degrees to the opposite side of the cylinder axis (in most cases, the handle of the Jackson cross cylinder lens should be aligned directly over the axis of the cylinder lens in the trial frame).

Instruct the subject to focus on an "O" or "C" one-two lines above the smallest line of letters that he can read.

Explain to the subject: *I am going to show you two views of this "C" and neither view may be clearer than the view you have right now. I would like to know which of the two views is the clearer of the two, or are both views pretty much about the same or equally blurry. Ask: Is the "C" clearer on view 1 [flip the lens] or view 2, or are both views about the same or equally blurred?*

- Since neither position may produce a clear image, the subject is encouraged to select the position of least blur.

If the subject cannot choose between the two positions of the cross cylinder at the beginning of this test, the axis of the cylinder is moved 5-15 degrees, first in one direction and then in the other, with the cross cylinder being checked in each position to confirm that the original axis was indeed correct.

- If the subject does prefer one position of the cross cylinder to the other, the axis of the cylinder is moved 5-15 degrees toward the positive axis of the cross cylinder when in the position the subject said was better.

When the power of the cylinder is low and/or the subject's discrimination is poor, larger shifts will produce more clear-cut responses.

The cross cylinder is tried again with the positive axis 45 degrees to one side of the new cylinder axis and then with the positive axis 45 degrees to the opposite side of the new cylinder axis; the subject is asked which position he/she prefers.

- If the subject prefers one position to the other, the axis of the plus cylinder is moved toward the positive axis of the cross cylinder.

Testing for change of axis is repeated until the subject cannot decide that one position of the cross cylinder is clearer than the other by reporting that both views are about the same or equally blurry.

1.7 Refine Cylinder Power

Change in cylinder power is now tested by adding the 0.25 D cross cylinder (or appropriate cross cylinder based on level of acuity), first with the positive axis and then with the negative axis coincident with the cylinder axis.

Again, instruct the subject to focus on an "O" or "C" one-two lines above the smallest line of letters that he can read or on the smallest line of letters he can read. Explain to the subject: *Once again I am going to show you two views of this "C" and neither view may be clearer than the view you have right now. I would like to know which of the two views is the clearer of the two, or are both views pretty much about the same or equally blurry. Ask: Is the "C" clearer on view 1 [flip the lens] or view 2, or are both views about the same or equally blurred?*

- If the subject prefers the positive axis coincident with cylinder axis, the power of the correcting plus cylinder is increased by an additional plus 0.25 D.
- If the subject prefers the negative axis coincident with the cylinder, the power of the cylinder is reduced by 0.25 D.

The process is repeated until the subject cannot choose one of the cross cylinder positions as better than the other (i.e., until both positions are about the same or equally blurred).

Whenever the cylinder is changed by 0.50 D, 0.25 D of sphere of opposite sign is added as well (the changing of the sphere occurs during the procedure as soon as the cylinder has been changed by 0.50 D rather than making the adjustment following the completion of the refinement).

1.8 Checking Cylinder When Beginning Refraction is a Sphere

If the beginning refraction is a sphere and does not contain a cylinder, the presence of astigmatism can be tested by one of two methods:

1. Instruct the subject to focus on a letter "C" or "O" one-two lines above the smallest line of letters that he can read. Arbitrarily place a plus cylinder (for plus cylinder refraction) appropriate for the current acuity at 90 degrees, 180 degrees, 45 degrees, and 135 degrees in the trial frame and ask the subject if the lens makes the "C" or "O" clearer. If the subject reports that the cylinder makes the "C" or "O" clearer in any of these locations, continue the refraction by modifying the cylinder axis and power as described above.
2. Arbitrarily insert a +0.25 cylinder (or power appropriate for the current acuity) into the trial frame at axis 90 degrees, 180 degrees, 45 degrees, and 135 degrees. *Using a Jackson Cross Cylinder* appropriate for the current acuity, check for cylinder power at 90 degrees, 180 degrees, 45 degrees, and 135 degrees. If the subject accepts the cylinder in any of these locations, continue the refraction by modifying the cylinder axis and power as described above.

1.9 Refraction Recheck/Final Sphere Refinement

The power of the sphere is rechecked according to the sphere refinement protocol above by using +0.37 D and -0.37 D spheres and changing the spherical power by 0.25 D increments of the appropriate sign until the subject reports that the +0.37 lens blurs the vision and the -0.37 does not improve vision. If the sphere is changed at this point by 0.50 D or more, the cylinder axis and power should be rechecked. This process is repeated until no further significant lens changes are made. In refractions using the phoropter and the EVA, a final check of the sphere as described above **must** be repeated using the EVA (at a distance of 3 meters) and trial frames.

The entire process is then repeated for the left eye.

1.10 Refraction for Subjects with Poor Visual Acuity

For subjects with acuity worse than 20/100, the strong preference is to use the EVA at 3 meters since letters can be projected as large as 20/800. The EVA chart is a three-meter chart and should not be moved closer to the subject.

When the ETDRS chart R is used, if the subject is unable to read at least 3 letters on both the 20/200 and 20/160 lines, the subject should be moved to 1 meter, a +0.75 diopter (D) sphere added to the spherical power in the trial frame, and the refraction performed using the appropriate lenses according to the vision level. The refraction obtained at 1 meter must be reported as a 4-meter equivalent by subtracting +0.75 (D) from the spherical power.

If the subjective refraction cannot be performed because the subject's visual acuity is too poor, then the subject's most recent distance subjective refraction obtained at a previous visit should be considered as the refraction.

[figure not shown]
Example 1: ETDRS chart R is used for refraction which could not be performed at 4 meters in the right eye because the subject could not see any letters on the refraction chart at that distance. When the subject was moved up to 1 meter, the following was obtained: + 2.00 + 1.00 x 180 degrees.

Example 2: ETDRS chart R is used for refraction which could not be performed at 4 meters in the right eye because the subject could not see any letters on the refraction chart at that distance. When the subject was moved up to 1 meter, the following was obtained: - 1.00 + 1.00 x 180 degrees.

In order to make this finding appropriate for visual acuity testing at 4 meters, a +0.75 D sphere must be subtracted from the above correction, resulting in -1.75 +1.00 x 180 degrees for the final refraction.

C. Refraction Protocol Summary

FLOW CHART OF REFRACTION PROTOCOL

NOTE: "Clearer, Blurrier, No Change" preferred; "Better, Worse, No change" may also be used.

Vision with Best Correction	Sphere		Cylinder			Sphere Refinement	
	Power (1)	Increment (1)	Axis (2)	Power (3)	Increment (3)	Power (4)	Increment (4)
20/20-20/80	+0.50	+0.50	a. .50 JCC	a. .25 JCC	+0.25 -0.25	a. +.37	+0.25
	-.50 - 0.37	-.25				b. -.37	-.25
	+0.50	+0.50				c. +.37	+0.25
<20/80-20/160	+1.00	+1.00	a. 1.00 JCC	a. 1.00 JCC	+1.00 -1.00	a. +.50	+0.50
	-1.00	-0.50				b. -.50	-.50
	+1.00	+1.00				c. +.50	+0.50
20/200 – 20/320	a. +2.00	+1.00	a. 1.00 JCC	a. 1.00 JCC	+1.00 -1.00	a. +1.00	+1.00
	b. -2.00	-1.00				b. -1.00	-1.00
	c. +2.00	+1.00				c. +1.00	+1.00
<20/320	a. +2.00	+1.00	No cylinder test			No refinement	
	b. -2.00	-1.00					
	c. +2.00	-1.00					

